#### 4.3 Randomization and baseline visit procedures

Randomization may occur upon confirmation that all inclusion/exclusion criteria are satisfied and after verification of participant consent and HIPAA authorization. Of particular importance, careful consideration will be given the patient's prior history of CHTN, current use of and adherence to antihypertensive therapy, and standardized clinic BP measurement to determine eligibility and the appropriate study algorithm to follow (see below). Study staff will also verify participant contact information and obtain a Release of Information, as permitted by local policy, to collect outcome and serious adverse event (SAE) documentation. Patients will be assigned to treatment groups with a concealed randomization allocation sequence using a web-based application managed by the Data Coordinating Center (DCC). Randomization will be stratified by clinical center to assure balance between treatment groups with respect to anticipated differences in the center population and possible differences in patient management. There will be 2 categories of patients with new or known mild chronic hypertension randomized:

a) Women with untreated CTHN: This group includes women with a new diagnosis of CHTN as well as women with a prior diagnosis of CHTN but not being treated. All of these patients must have pragmatic

clinic BP 140-159/90-104 to be eligible for randomization. (\*\*Note that criteria for a new diagnosis of chronic hypertension includes elevated BPs on at least 2 occasions a minimum 4 hours apart; a diagnosis of known chronic hypertension is based on current or prior antihypertensive therapy for a diagnosis of chronic hypertension).

- b) Those on a single antihypertensive agent who are adherent with their meds:
  - Adherent with medications defined as having taken medication within the last 24 hours of randomization.
  - BP inclusion range will be standardized pragmatic SBP ≤159 and DBP ≤104 for a woman in this group (including those with BP<140/90).

The enrollment BPs will be based on the single blood pressure <140/90 or the repeat blood pressure measurement (if ≥140/90) for clinical decision making (pragmatic clinic BP).

If a pragmatic clinic BP is not available for any reason, the automated/OMRON BP may be used to determine entry.

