## 5.3.1 Primary Aims

Standard comparisons of characteristics between groups will be conducted at baseline. It is anticipated that the randomization scheme will balance the groups for these covariates (considering the large sample size) and they will not be adjusted for in the primary analyses. However, secondary analyses of relevant outcomes using regression adjustments will be implemented to account for any suggested confounding covariates that are unbalanced between study groups. The potential adjustment covariates include baseline BP level, race/ethnicity, smoking status, prior anti-hypertensive use (known CHTN), gestational age at baseline and weight. Per protocol analyses, which reflect adherence to antihypertensive therapy will be conducted in secondary analyses.

The primary analysis will compare the incidence of the composite outcome and SGA between the 2 study groups – a chi-square p-value and the RR and 95% CI (relative to ACOG comparison group) will be computed and followed up with a logistic regression comparison which will take into account the duration of therapy, GA at initiation of therapy and other covariates. Event free survival will be calculated using Kaplan Meier estimates and tested using a log rank test. Student's t-test comparisons of continuous outcomes (duration of hospital, NICU stay, etc.) will be conducted.

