### 2. DESCRIPTIVE ANALYSES

Patient characteristics at baseline will be summarized by randomization group. The two study groups will be labeled as Lower (for primary BP lowering therapy with labetolol or nifedipine ER) and Standard (for ACOG standard treatment). For continuous variables, means/medians and standard deviations (or interquartile ranges) will be reported. To assess and/or identify covariates for which adjusted sensitivity analyses might be conducted, student t-tests will be used to compare means between study groups. Where appropriate, medians and quartiles will be reported and the Wilcoxon rank sum test will be used as an

alternative comparison procedure. Categorical measures will be presented as counts and percentages and will be compared using the  $\chi^2$  tests of association to identify potential group differences. For rare outcomes such that the  $\chi^2$  test of association is not appropriate, Fisher's exact test will be used. Balance overall is expected because of the large sample size and we expect approximately 5% to be different by chance, since we are not adjusting these baseline comparisons for multiple testing. Any group characteristics that are identified as statistically significantly different between the two groups at a 0.05 level of significance will be considered as covariates in multivariable models in subsequent analyses of the primary study outcome.

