3.1.2. Analysis Plan: This hypothesis examines the effectiveness of structured blood pressure treatment (Lower BP group) for mild chronic hypertension in pregnancy versus usual care (Standard BP group). The  $\chi^2$  test of association will be used to evaluate whether the rate of the primary outcome differs between the two blood pressure management approaches. The primary analysis will follow an intention-to-treat (ITT) approach of all individuals randomized to the two treatment groups, regardless of whether they adhered to their assigned treatment. For cases where the primary composite outcome is undetermined (for example, dropout prior to delivery), the primary analysis will utilize multiple imputation for the primary outcome. Missing values will be estimated using characteristics within each treatment group that may be predictive of the composite outcome. Specifically, a logistic regression model will be fit within treatment group using baseline characteristics including diabetes status (yes/no), treatment status at enrollment (on BP meds vs. not on BP meds), age, BMI, and elevated BP at the first visit (SBP  $\geq$  150 and/or DBP  $\geq$  100). Multiple imputed data sets will be developed and up to 5 replicates will be considered. The primary analysis will be conducted on each of the imputed complete data sets and the final results will be pooled.

A sensitivity analysis will include all individuals for whom a primary outcome can be assessed (a complete-case analysis) in a modified ITT approach. Our expectation is that on a small fraction (<10%) of the dataset will require imputation and thus the complete case analysis will agree substantially with the primary imputation-based analysis.

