Risk ratios (RR) and 95% confidence intervals (CIs) will be computed and presented, as well as individual group rates and 95% CIs. Standard comparison of the covariate characteristics at baseline between study groups will be undertaken (Section 2) to assess the randomization balance on measured covariates. Tests of significance will be two-sided and evaluated at the 0.05 level of significance. Since the sample size for CHAP is large, it is unlikely that "important" covariates (such as race, BMI or age) will be imbalanced through the randomization process. However, in the unlikely event that this occurs, adjustment for covariates will be made by modeling the log-odds of the outcome using multivariable logistic regression including terms indicating group membership, site and each of the imbalanced covariates. In other words, the log-odds of the primary outcome for any individual will be modeled using the following form:

$$\ln\left(\frac{P(outcome)}{1-P(outcome)}\right) = \beta_0 + \beta_1 x_1 + \sum \beta_j z_j.$$

Above,  $x_l = 1$  if the patient is in the Lower BP group (treatment) and equals 0 if the patient is in the Standard BP group (no-treatment). The set of  $z_j$ 's consists of all covariates in the model including site. Hence, under this model, the term  $\beta_l$  represents the difference in the log-odds between the two groups. To address the hypothesis of interest for primary hypothesis #1, we will perform a statistical test of  $H_0$ :  $\beta_l = 0$  vs.  $H_1$ :  $\beta_l \neq 0$ . Quantification of the treatment effect will be performed by exponentiation of the estimated coefficient,  $\exp(\beta_l)$ , to obtain an estimate of the odds ratio. The confidence interval will be determined similarly. The presence of a homogeneous center effect will be examined with inclusion of study center as strata using the Breslow-Day test. Generalized estimating equations to account for repeated measures within sites may be considered as well, especially in the event that significant center effects are detected. Modified Poisson regression modeling with robust standard errors will also be considered in order to estimate risk ratios for the primary outcome while adjusting for any possible covariates. While logistic regression yields odds ratios that often approximate risk ratios, direct modeling of risk ratios may yield more informative estimates of the true risk of the outcome.

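### SAP 3.1.2 and 3.2.2 misstate the deciding test, its level and the SGA imputation trigger; stratifying by center and fixing the imputation number are cheap improvements

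*Combined protocol and SAP*

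**What the plan says.** - **Test.** SAP 3.1.2 says that a chi-square "test of association will be used to evaluate whether the rate of the primary outcome differs between the two blood pressure management approaches". SAP 3.2.2 uses the same test for SGA. SAP 3.3 and protocol 5.3.3 read the composite's chi-square against 9 (p < 0.0027) at the interim and 3.87 (p < 0.0492) at the end. None of these uses center, although protocol 4.3 says "Randomization will be stratified by clinical center to assure balance between treatment groups".
- **Level and adjustment.** SAP 3.1.2 also says "Tests of significance will be two-sided and evaluated at the 0.05 level of significance". If important covariates are imbalanced, "in the unlikely event that this occurs, adjustment for covariates will be made by modeling the log-odds of the outcome using multivariable logistic regression", with site and the imbalanced covariates as terms. It continues "To address the hypothesis of interest for primary hypothesis #1, we will perform a statistical test of" a zero treatment coefficient. Protocol 5.3.1 says of baseline covariates that "they will not be adjusted for in the primary analyses" and offers a list: "The potential adjustment covariates include baseline BP level, race/ethnicity, smoking status, prior anti-hypertensive use (known CHTN), gestational age at baseline and weight". SAP 2 compares baseline characteristics "To assess and/or identify covariates for which adjusted sensitivity analyses might be conducted" and selects them at 0.05.
- **Imputation.** SAP 3.1.2 imputes an undetermined composite within arm, allows at most five replicates and pools the results. It gives no minimum number, no seed and no rule for pooling a chi-square.
- **SGA.** SAP 3.2.2 imputes SGA when the composite is undetermined, and gives loss before delivery as the example. Under SAP 3.1.1 a single component event settles the composite, which counts severe preeclampsia to two weeks postpartum and neonatal death to 28 days.

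**The concern.** A confirmatory analysis needs one test, one level and one rule for missing data. SAP 3.1.2 gives hypothesis #1 a second test, run only after an imbalance is seen, and a level that differs from the final boundary. A result near the threshold could then be argued two ways. The SGA rule names the wrong outcome. Applied literally, it could impute values already recorded for the primary safety outcome and leave some missing ones without a rule.

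Two further choices give something away. The tests ignore the factor used to stratify randomization, and so few imputations let a near-threshold verdict depend on the random seed.

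**Working it through.** **1. Boundaries (SAP 3.3).** The 1-df chi-square tail is 0.0027 beyond 9 and 0.0492 beyond 3.87, as stated. The interim is at 1202/2404 = half the information, so the two z statistics correlate at √0.5. Overall error = P(|Z1| > 3 or |Z2| > 1.967) = 0.0500, which reproduces the plan. With 1.960 (p < 0.05) at the final look it is 0.0508. A final p between 0.0492 and 0.05 has probability 0.0008 (0.08%) under the null and 0.28% at a 25% effect.

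**2. Triggered test.** With k independent covariates screened at 0.05, at least one is flagged with probability 1 − 0.95^k: 14% for k = 3, 26% for 6, 40% for 10 and 64% for 20. The plan does not fix k. In simulation (1.5 million draws, k = 3 or 6, cut-off 3.87):
- Claiming success on either test when triggered moves null rejection from 4.92% to 4.99-5.15% with no site effect, and from 4.23-4.25% to 4.34-4.54% when site explains 6% of variance.
- If the adjusted test simply replaces the chi-square when triggered, the error is 4.3-4.9%.
- The two tests disagree in 0.15-0.5% of null trials.

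**3. SGA trigger, read literally.**

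| Composite | SGA recorded | SGA missing |
|---|---|---|
| Undetermined | imputed, although known | imputed |
| Determined | kept | no rule |

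The top-left cell can arise because the composite window extends past delivery. The bottom-right cell arises when an event has occurred but there is no birth weight. Planned attrition (SAP 3.1.4) is 0.05 × 2404 = 120 women, not split into before and after delivery.

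**4. Center.** Inputs from SAP 3.1.4: 16% control rate, 33% reduction (0.16 × 0.67 = 10.72%), 10% noncompliance and 10% crossover. The diluted rates are 0.9 × 16 + 0.1 × 10.72 = 15.47% and 0.9 × 10.72 + 0.1 × 16 = 11.25%. There were 40,000 simulated trials per setting, with 16 or 30 centers, about 2284 women and cut-off 3.87. The between-center SD is assumed, since the documents give none.

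| SD (log-odds) | Power gain from stratifying, points | Null rejection, chi-square |
|---|---|---|
| 0 | 0.0 | – |
| 0.25 | 0.11-0.17 | 4.77-4.85% |
| 0.5 | 0.57-0.70 | 4.46-4.71% |
| 0.75 | 1.14-1.45 | 4.09-4.40% |

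The stratified (Cochran-Mantel-Haenszel, CMH) test rejects 4.80-5.06% under the null over SD 0.25-0.75.

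**5. Number of imputations.** SAP 3.1.2 expects under 10% imputed, so take a fraction of missing information (FMI) of 0.05 to 0.10. Relative efficiency at m = 5 is 1/(1 + FMI/5) = 0.990 to 0.980. On fixed data, the pooled z varies between reruns with SD √(FMI/m): 0.100-0.141 at m = 5 and 0.032-0.045 at m = 50.

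The expected z with 1142 per arm is (difference)/√(2p̄(1 − p̄)/1142). At a 33% effect it is 2.967. At 25% (15.6% vs 12.4%, SAP 3.1.3) it is 0.032/0.01452 = 2.204. Two reruns fall on opposite sides of 3.87 in:

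| Effect | m = 5 | m = 50 |
|---|---|---|
| 33% | 2.7-3.9% | 0.9-1.2% |
| 25% | 4.4-6.2% | 1.4-2.0% |
| none | 1.3-1.9% | 0.4-0.6% |

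A p of 0.049 (z = 1.969) at m = 5 reruns (±1 SD) as 0.039-0.062 with FMI 0.05 and 0.035-0.068 with FMI 0.10. A direct imputation simulation (150 datasets per setting, 12 reruns each) gave a larger SD with 10% missing, 0.178 against the formula's 0.141, which widens the second range to 0.032-0.073. Its rerun disagreement at m = 5 was 1.8% (SE 0.7) with 5% missing and 4.2% (SE 1.0) with 10% missing.

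**The case against.** The unstratified chi-square is a legitimate choice. It holds its level and is slightly conservative when centers differ, and nothing in the documents requires a stratified test. That stands: stratification is an improvement, not a correction. The Breslow-Day test and optional GEE in SAP 3.1.2 do attend to center, but the first checks homogeneity of effect and the second is only a possibility, so neither makes the deciding test stratified.

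On the level, SAP 3.3 is the specific rule, and 0.05 equals the overall error it protects. Protocol 5.3.1 also puts the chi-square first and has logistic regression follow. This shows the likely intent, but SAP 3.1.2 still attaches the triggered test to hypothesis #1.

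On SGA, the example of loss before delivery, and the instruction to follow the composite's plan, suggest that missing SGA was meant. The operative condition still says otherwise.

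On imputation, five replicates keep 98-99% efficiency, the trial is analysed once, and 50 is a convention. What remains is reproducibility of the verdict.

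A reader might infer that ignoring center or switching tests seriously inflates type I error, or that some 120 recorded SGA values will be overwritten. The documents support neither. Steps 1, 2 and 4 show negligible inflation, and 120 is a ceiling; the true number could be near zero.

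**Conclusion.** Two texts are wrong as written: the level and triggered test in SAP 3.1.2, and the SGA imputation trigger in SAP 3.2.2. The first matters only near the threshold (overall alpha 0.0508 against 0.0500). The second affects an unknown number of women.

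Center stratification is worth about 0 to 1.4 power points, and only 0.1-0.2 at an SD of 0.25; the whole range rests on an assumed SD. More imputations cut rerun disagreement roughly threefold at the planned effect. That rests on 5-10% missing information and on a variance formula that the direct simulation suggests is somewhat optimistic at 10% missing. The planned complete-case and best- and worst-case analyses would reveal fragility but would not settle which result is primary.

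**What to change.** 1. **SAP 3.1.2 and protocol 5.3.1.** State that one primary test without covariate adjustment decides the composite, at 0.0492 at the final look. Label the logistic model supportive. Fix its covariates in advance from the protocol 5.3.1 list, reconciled with the age, BMI and site named in SAP 3.1.2, and drop selection at p < 0.05.
2. **SAP 3.2.2.** Trigger SGA imputation on missing SGA status, whatever the composite status.
3. **SAP 3.1.2 and 3.2.2.** Fix a larger number of imputations (for example 50) with a recorded seed.
4. **Optional stratification.** Stratify by center, merging very small or one-arm centers by a rule set on blinded data.
5. **One statistic.** Name a single deciding statistic for the imputed analysis. An example is the Rubin-pooled 1-df Wald chi-square of the center-stratified log Mantel-Haenszel risk ratio, read against 9 and 3.87, with complete-data CMH as a sensitivity check. The pooled procedure's null rejection rate has not been checked here and should be confirmed by simulation.

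The cost is rewording (including SAP 3.3 and protocol 5.3.3 if the statistic changes), a few lines of code, computing time and the approvals in protocol 1.4: Steering Committee and IRBs, plus the DSMB if the change counts as major. No new data are needed. If the interim has already been read on the unstratified chi-square, a complete-data stratified final test at 3.87 still gave 4.86-5.13% overall error in simulation (SD 0.25-0.75, Monte Carlo SE 0.1 point). Items 1 to 3, and a named pooled statistic, can be adopted without stratification.

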#### 5.2 Power for other outcomes

The sample size of 2404 provides adequate power to examine SGA and key secondary outcomes. The corresponding power for each outcome considering conservative estimates of baseline incidence and effect sizes given a 2-sided alpha of 0.05 are shown in Table 7.

Table 7: Power – SGA and Secondary Outcomes

Outcome	Incidence	Effect size %	Power
SGA	10-14%	35-40	≥85%
Preeclampsia	20%	25	>85%
Cardiovascular	4-6%	50	80-90%
Preterm birth	20%	25	>85%
Perinatal death	4-6%	50	80-90%

The baseline risks of SGA, preeclampsia, preterm birth and perinatal death are likely to be higher considering the reviewed literature and our preliminary data--power may actually be higher. The incidence of the rare maternal cardiovascular outcome is not well characterized. This study will provide an estimate. Finally, regarding the repository, we anticipate collecting baseline and follow-up biospecimens (especially maternal and cord blood) on ≥80% (n=1920).

c) Baseline/covariate information: These will include demographics (age, parity, ethnicity, education, profession, payor), entry GA at entry, entry BP, duration of CHTN, treatment status on entry, prior preeclampsia, prior fetal death, BMI, smoking/alcohol/drug use.

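### SAP 3.1.2 imputes an undetermined primary composite from baseline predictors alone, so women lost late and event-free are given too high a risk

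*Combined protocol and SAP*

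**What the plan says.** SAP 3.1.2 sets the rule for missing primary outcomes: "where the primary composite outcome is undetermined (for example, dropout prior to delivery), the primary analysis will utilize multiple imputation". The method is that "a logistic regression model will be fit within treatment group using baseline characteristics including diabetes status (yes/no", followed by whether the woman was on BP medication at entry and by "age, BMI, and elevated BP at the first visit". All five named predictors are fixed at or before entry. The list is introduced by *including*, so it is not stated to be closed.

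The SAP does not say when a composite counts as undetermined if some components are already known. It names neither gestational age at last contact nor delivery status, and no rule limits what may be imputed. It expects that only a "small fraction (<10%) of the dataset will require imputation".

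Under SAP 3.1.1 the composite is positive as soon as any one component occurs. Protocol 4.7.6 runs ascertainment of the primary outcomes through the delivery discharge and two weeks postpartum. Other treatments of missing outcomes are a complete-case analysis (SAP 3.1.2) and best-case and worst-case scenarios (a later paragraph of the same section). SAP section 4 adds a Kaplan-Meier and log-rank analysis.

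**The concern.** The fact of being undetermined carries information. A woman whose event was seen before she left is determined, and positive. A woman who is undetermined has had no observed event up to her last contact. The imputation model is fitted to determined women, who include all the observed early events, and is then applied to women who have already passed part of the risk period.

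The gap is widest for late losses: women last seen event-free after 35 weeks, or delivered after 35 weeks and lost before two weeks postpartum. Indicated preterm birth before 35 weeks, the most frequent component in the planning data, is no longer possible for them. A baseline-only model still gives them the average probability for their arm and covariates. Given baseline alone, the missing-at-random assumption is hard to defend for these women.

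At stake are the reported arm rates, which would be too high, and the risk difference, which would be slightly too wide because late losses receive the full arm difference.

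**Working it through.** **Inputs**
- Composite rate C = 16%; indicated preterm birth before 35 weeks D = 12.32% (protocol 5.1.1, SAP 3.1.3, taken from an earlier aspirin trial).
- Reduction 33%, attrition 5%, 1202 per group (protocol 5.1.2, SAP 3.1.4).
- Missing share m: 5% (planned attrition) to 10% (the SAP's upper limit).
- Late share f, the fraction of missing women last known event-free after 35 weeks: not in the documents. Assumed 25-50%, with 100% as ceiling.
- Lower arm: the 33% reduction is applied to each component (assumption).

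**The plan's own figure.** The usual two-proportion formula (pooled variance, two-sided 0.05, 85% power) gives 745 per arm for 16% against 10.72%; the plan has 748. After dilution the rates are 0.9 × 16 + 0.1 × 10.72 = 15.47% and 0.9 × 10.72 + 0.1 × 16 = 11.25%, which give 1164; the plan has 1142. Then 1142 / 0.95 = 1202.1, as stated. No sample-size figure is in dispute here.

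**Step 1: remaining risk once D is ruled out, (C − D) / (1 − D)**
- Standard: (0.16 − 0.1232) / (1 − 0.1232) = 0.0368 / 0.8768 = 4.20%. The model gives about 16%, which is 3.8 times as much. Gap 11.80 points.
- Lower: C = 10.72%, D = 0.67 × 12.32% = 8.25%. (0.1072 − 0.0825) / (1 − 0.0825) = 2.69%. Gap 8.03 points.

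This formula assumes that every composite event without indicated preterm birth before 35 weeks is still possible after 35 weeks. Any that fall earlier would lower the remaining risk and widen the gap.

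**Step 2: excess expected events = 1202 × m × f × gap**

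| m | f | late losses per arm | excess, Standard | excess, Lower | points, Standard / Lower |
|---|---|---|---|---|---|
| 5% | 25% | 15.0 | 1.8 | 1.2 | 0.15 / 0.10 |
| 5% | 50% | 30.1 | 3.5 | 2.4 | 0.30 / 0.20 |
| 10% | 25% | 30.1 | 3.5 | 2.4 | 0.30 / 0.20 |
| 10% | 50% | 60.1 | 7.1 | 4.8 | 0.59 / 0.40 |
| 10% | 100% (ceiling) | 120.2 | 14.2 | 9.7 | 1.18 / 0.80 |

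**Step 3: effect on the comparison**
- Risk difference, planned at 16 − 10.72 = 5.28 points. Too wide by 0.15 − 0.10 = 0.05 points (5% missing, 25% late) to 0.59 − 0.40 = 0.19 points (10%, 50%).
- Risk ratio, equal missingness: 0.67 with baseline-only imputation and 0.67 with conditional imputation.
- Risk ratio, unequal missingness, half late: with 5% missing in Standard and 10% in Lower, conditional imputation gives 0.1032 / 0.1570 = 0.657. With the shares reversed it gives 0.1052 / 0.1541 = 0.683. Baseline-only imputation gives 0.67 both times.
- Same missing shares with no true effect: 0.98 and 1.02 against 1.00.

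**Step 4: sensitivity to C.** The blinded reassessment found a higher overall rate than planned but does not report it. With D unchanged and C at 20% or 30%, the remaining risk is 8.8% or 20.2%, and the gap is 11.2 or 9.8 points. The Standard-arm gap is therefore fairly stable.

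**The case against.** The strongest reply is that the treatment effect barely moves. That stands: the risk ratio does not change under balanced dropout and shifts by 0.01-0.02 under fairly unequal dropout.

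The number of late unknowns may also be small. Protocol 3.4 excludes women unlikely to follow up or planning to deliver outside the consortium centers. Section 4.3 obtains a release of information where local policy allows, and 4.5 relies on record abstraction through discharge. This stands too. The late share is unknown and the excess shrinks in proportion to it.

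The component split comes from a trial with a narrower definition of severe preeclampsia (0.66%) than protocol 4.7.1 uses, so this trial's mix may differ. Step 4 covers a higher composite rate with D unchanged. A lower D would narrow the gap.

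The plan has safeguards, but none corrects this point. Complete-case analysis drops event-free late losses while keeping early events, so it shares the selection, and its agreement with the imputed result would not be reassuring. The best and worst cases bound the effect, but they set about 60 women per arm (5% of 1202) to all events or none and ignore what was seen. Kaplan-Meier can use event-free time but is only an additional analysis.

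A reader might infer more than the documents support:
- *That only five variables may be used.* The list is open. The weakness is that the named predictors are all baseline, not that there are five.
- *That the model imputes births before 35 weeks to women known to be past 35 weeks, contradicting the data.* It imputes composite status. Death, abruption and severe preeclampsia remain possible, so an imputed event contradicts nothing; its probability is too high.
- *That omitting center and obstetric history is itself an error.* The protocol states "Randomization will be stratified by clinical center to assure balance between treatment groups" and lists among collected items "entry GA at entry, entry BP, duration of CHTN, treatment status on entry, prior preeclampsia, prior fetal death, BMI". But the primary test is an unadjusted chi-square, and 16 or more centers in within-arm logistic models could produce sparse cells. Adding these predictors is a matter of preference.

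**Conclusion.** The point holds as a limited upward bias in the arm rates. As written, the primary imputation ignores observed event-free follow-up and gives late losses about 16% in the Standard arm where about 4% is left on the planning rates. With 5-10% missing and 25-50% of losses late, that is about 2-7 excess expected events in the Standard arm, 1-5 in the Lower arm, and 0.05-0.19 points on the risk difference. The 2-7 range must not be read as applying to each arm.

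The size rests on the assumed late share, the borrowed component rates, and a 33% reduction common to all components. A reader might infer that the primary conclusion is at risk; the figures do not support that. The change is worth making because it is cheap and can be pre-specified.

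**What to change.** In SAP 3.1.2:
1. Define when the composite is undetermined, including the case where some components are known.
2. Keep every observed component value.
3. Condition the imputation on gestational age at last event-free contact and on delivery status, and impute only the components still possible. For late losses, for example, fit the within-arm model among women event-free at that gestational age.
4. Optionally add gestational age at randomization, prior preeclampsia and prior fetal death. Add center only if cell counts allow.

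The cost is a few lines of SAP text and modest programming; protocol 6.1 already lists prenatal visit, delivery, postpartum and participant-status forms. The downside is a more complex model fitted to fewer events. On the planning rates about 1202 × 0.0368 = 44 Standard-arm and 1202 × 0.0247 = 30 Lower-arm events remain after 35 weeks, so the late-loss model should stay small.
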